### 4.2.2 Study Population

The study population will be recruited from a number of sources:

- (a) Direct referrals from health professionals within any NHS Hospital Trust or primary care practice. Regular news letters will be sent to professional societies / Clinicians / NHS Trusts / GP practices, to disseminate project specific information. The flowchart in **Appendix 2** of the protocol demonstrates the recruitment via direct health professional referral.
- (b) Searching hospital database records and case notes to identify potential participants. Research nurses working on the project will actively search for eligible patients.
- (c) Direct approach to previous study populations known to have experienced ADRs, via the healthcare professionals normally involved in the care of the patient.
- (d) The Yellow Card Reporting System. Following approval of this method of recruitment by the MHRA, we will utilise the yellow card database to identify potential patients. The flowchart in **Appendix 5** of the protocol demonstrates the recruitment process via the Yellow Card Reporting System.
- (e) Referrals from industry partners via health professionals from clinical research facilities.
- (f) Direct referrals from private healthcare providers.
- (g) Imported samples from national and international collaborators collected under their own protocols and ethical approvals which have permission to share and ship samples. Cryopreserved peripheral blood mononuclear cells and other relevant biological samples collected will be transferred to Liverpool using an MTA stating that the external samples will be used to contribute to analysis for HYST.

### 4.2.3 Withdrawal of Subjects

Subjects will be informed that they are free to withdraw from the study at any time. Subjects may ask for their samples to be destroyed up to the time the samples and data are coded but not anonymised. However, once the sample is fully anonymised, this will not be possible. The Investigator may remove a subject if, in his / her opinion, it is in the best interests of the subject. If a patient permanently withdraws from the study, or is lost to follow-up, the reason will be recorded.

Protocol V17 07.02.2023

#### **4.2.4 *Loss to follow up***

If any of the study patients are lost to follow up, contact will initially be attempted through the pharmacology research nurses at each participating NHS site. If the Principal Investigator at the study NHS site is not the patient's usual clinician responsible for their speciality care then follow-up will also be attempted through this clinician. Where all of these attempts are unsuccessful, the patient's GP may be asked to provide follow-up information to the recruiting centre.

#### **4.2.5 *Co-enrolment Guidelines***

Patients registered for the Hypersensitivity study are not restricted to entry onto any other clinical trial, study or research project as this study consists of blood sampling. However information regarding any trial participation will be collected on the follow-up CRF forms.

#### **4.2.6 *Concomitant medications***

There are no restrictions on medication for this study. All current medications and medications taken at time of reaction will be recorded in the CRF.

## **5. Sampling and Data Collection**

### **5.1 Blood Sampling**

Hypersensitive patients and patients that can tolerate the drug of interest without hypersensitivity reactions will also be recruited; the samples provided by this control patient cohort will act as experimental controls.

The adult patients will be asked initially to provide 50mL venous blood sample from which we will isolate the plasma and mononuclear cells using density gradient centrifugation. The volume of blood from paediatric patients will be less than this, and will conform to EMA guidelines and will not exceed 1% of total body circulating volume at a single sample, or 3% in a 4 week period. The current laboratory techniques require a minimum volume of blood for a successful sample analysis, although this will decrease as the technologies evolve during the study period. Children and young people whose weight requires a sample less than the minimum volume required for successful analysis will not be recruited. The minimum volume required will be determined by regular consultation with the laboratory team during the study. When biological samples including peripheral blood mononuclear cells (from hypersensitive and tolerant patients) are imported from collaborators under their own protocols and ethical approval, cells will be cryopreserved at the collaborating site and transported in a cryogenic environment (eg. dry ice, liquid nitrogen). The cells will be defrosted in Liverpool and used in the same way as samples collected from other sources in the experiments described below.

Protocol V17 07.02.2023

Plasma will be used for bioanalysis; DNA will be used for HLA typing and profiling drug specific changes in gene expression. Cells will be used for:

- (a) Standard lymphocyte proliferation assays and an assay that incorporates a metabolising system.
- (b) Generation and characterisation of drug specific T cell clones.
- (c) Generation of immortalised Epstein-barr virus transformed B cell lines to be used an autologous population of antigen presenting cells.

Storage in liquid nitrogen to restimulate responding T cell lines and clones as and when required. Adult patients that produce the most vigorous response in the lymphocyte transformation test (LTT) may be asked to donate further blood samples; the patients that are re-called will be asked to donate up to 60mL of venous blood. We believe it is important to make these patients aware of the LTT result to their medication(s), so that severe reactions can potentially be avoided in the future. Paediatric patients will be assessed on a case by case basis. Any further requests for blood samples will be guided by the EMA guidelines (and the wishes of the patient/family) but will not exceed 3% total circulating volume in a 4-week period (approx. 2.4ml/kg).

For patients taking oncological immunotherapies, those displaying hypersensitivity and those tolerant to the drug will both be recruited. The samples provided by this control patient cohort who do not display hypersensitivity will act as experimental controls. Patients receiving PD-1 inhibitor monotherapy or in combination with a CTLA-4 will be recruited into the study.

The adult patients will be asked to donate up to 50mL venous blood samples (schedule seen in 5.1.2.2) from which we will isolate the plasma and mononuclear cells using density gradient centrifugation. This arm of the study will not be recruiting paediatric patients

Samples will be analysed as follows:

- a. Whole blood (including PBMCs post isolation) samples will be analysed for the presence of T-cell populations and subpopulations, cell surface and intracellular immune markers using Mass Cytometry using Time of Flight technology (CyTOF) and/or Flow cytometry
- b. Whole blood samples and PBMCs (isolated from whole blood) will be analysed for the presence of cytokines using CyTOF
- c. Plasma will be used for cytokine analysis using cytokine arrays and ELISA techniques
- d. Serum will be used to determine the presence of autoantibodies utilising protein array technology and ELISA techniques
- e. Transcriptomic analysis
- f. HLA typing

### ***5.1.1 Pharmacokinetic sub-study to investigate hapten formation and clearance***

The following outlines a detailed sampling procedure for the purpose of beta-lactam antibiotic hapten formation and clearance assessment. For other types of drugs, we would follow a similar procedure and ensure that no more than 20 samples (4mL per sample) are collected over 3 weeks.

- (a) Blood sampled in this sub-study will be collected into lithium/heparin coated vacuettes.
- (b) Blood will be sampled a maximum of 4 times a day; each blood sample will not exceed 4mL.

Protocol V17 07.02.2023

- (c) Sampling will be performed / defined on the basis of Cmax for the drug under study to enable blood to be sampled on the basis of peak and trough measurements of the free drug. Peak measurements will be taken 5 minutes after the drug had been administered intravenously; this will be in keeping with Tmax for drugs administered in this way.
- (d) Peak and trough blood sampling will be conducted twice a day for 2 days (i.e, 4 samples per day). For the following three days, blood sampling will be conducted to obtain two subsequent trough samples (i.e 2 samples per day) that will not exceed 4mL. Trough blood samples will be taken just before the administration of the next dose of drug.
- (e) After this initial 5-day period of blood sampling, blood will be sampled once a week for 3 weeks after the treatment has finished; the samples will not exceed 4mL. This is to measure the clearance of the drug-haptenated protein. During this time patients may have been discharged from hospital and, therefore, patients will be reimbursed reasonable travel expenses.
- (f) Plasma, required for bioanalysis, will be isolated within 60 minutes of each blood sample being taken, or as close as possible to this time point

Please note that on the basis of the initial assessments, participant availability and flexibility, we may change the sampling schedule but we will keep the total number of samples per patient constant. We will not exceed the total number of samples stated (seventeen samples (52 mls in total) over a four week period); however on occasion we may not obtain the full set of samples due to participant availability, withdrawal or Loss to Follow Up.

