**Days 0/1-2: Preliminary Blood Samples**

1. Consent	Verbal consent for continuation in the study
2. Blood sampling	1 blood sample (4mL) immediately prior to drug dose = trough measurement
3. Blood sampling	1 blood sample (4mL) 5 minutes after drug dosing = peak measurement
4. Blood sampling	1 blood sample (4mL) immediately prior to subsequent drug dose = trough measurement
5. Blood sampling	1 blood sample (4mL) 5 minutes after drug dosing = peak measurement

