**Days 3-5: Secondary Blood Samples**

1. Consent	Verbal consent for continuation in the study
2. Blood sampling	1 blood sample (4mL) immediately prior to drug dose = trough measurement
3. Blood sampling	1 blood sample (4mL) immediately prior to subsequent drug dose = trough measurement

[figure not shown]

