**Weeks 2-4: Single weekly blood samples**

1. Consent	Verbal consent for continuation in the study
2. Blood sampling	1 blood sample (4mL)

For patients taking oncological immunotherapies Plasma drug concentration samples will be taken prior to commencement of treatment, on the day of the initial treatment at Cmax, day 7, day 14 and day 21 of the initial treatment cycle. This is in keeping with the rest of the cohort schedule (Section 5.1.2.2.2) and will be taken at the same time.

[figure not shown]
Protocol V17 07.02.2023

**12.5 Appendix 5:** Flow chart for recruitment via direct healthcare professional referral

Protocol V17 07.02.2023

**12.6 Appendix 6:** Flow chart for recruitment from previous studies

Protocol V17 07.02.2023

[figure not shown]

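### Section 5.1.1 gives 52 mL for seventeen samples, but seventeen draws at the scheduled 4 mL come to 68 mL

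*Protocol*

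**What the plan says.** Protocol section 5.1.1 sets out the sampling for beta-lactam hapten formation and clearance.

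- **Volume per draw, item (b):** "each blood sample will not exceed 4mL".
- **First two days, item (d):** "Peak and trough blood sampling will be conducted twice a day for 2 days (i.e, 4 samples per day".
- **Next three days, item (d):** "For the following three days, blood sampling will be conducted to obtain two subsequent trough samples (i.e 2 samples per day) that will not exceed" 4 mL.
- **Clearance phase, item (e):** "blood will be sampled once a week for 3 weeks after the treatment has finished", again with 4 mL as the limit.
- **Overall commitment, closing paragraph:** "We will not exceed the total number of samples stated (seventeen samples (52 mls in total) over a four week period".

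Section 5.1.2.3 names Appendix 4 (section 12.4) as the visit schedule for this sub-study. The appendix gives the draw volume as a plain 4 mL, not as an upper limit. The Days 0/1-2 block has, for example, "1 blood sample (4mL) 5 minutes after drug dosing = peak measurement", and the Days 3-5 block has "1 blood sample (4mL) immediately prior to drug dose = trough measurement". The block headed "Weeks 2-4: Single weekly blood samples" also lists a 4 mL sample.

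**The concern.** The closing sentence of section 5.1.1 pairs a number of samples with a total volume. The number follows from the schedule; the volume does not follow from that number and the 4 mL draw. Both figures sit in a sentence that promises a limit, so a site or an ethics committee can fairly read 52 mL as the most blood a participant will give in this sub-study. A site that takes the daily counts in item (d), the weekly draws in item (e) and the draw volume in Appendix 4 will pass that figure in every participant who completes the schedule.

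What is at stake is the accuracy of a stated participant burden. No endpoint, estimate or sample size is affected.

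**Working it through.** **Inputs**

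| Quantity | Value | Source |
|---|---|---|
| Peak-and-trough days | 4 draws/day × 2 days | 5.1.1(d) |
| Trough-only days | 2 draws/day × 3 days | 5.1.1(d) |
| Clearance phase | 1 draw/week × 3 weeks | 5.1.1(e) |
| Volume per draw | 4 mL (a maximum in 5.1.1; stated flatly in Appendix 4) | 5.1.1(b), (d), (e); Appendix 4 |
| Stated totals | 17 samples, 52 mL | 5.1.1, closing paragraph |

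**Step 1: the stated count.** (4 × 2) + (2 × 3) + (1 × 3) = 8 + 6 + 3 = 17. This reproduces the protocol's figure.

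**Step 2: the stated volume.** 17 × 4 mL = 68 mL. This does not reproduce 52 mL. The difference is 68 − 52 = 16 mL, and 16/52 = 31%.

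**Step 3: when the total is passed.** The first five days hold 8 + 6 = 14 draws, and 14 × 4 = 56 mL. The stated total is already exceeded before any clearance sample.

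**Step 4: what 52 mL would fit.**

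- At 4 mL per draw, 52/4 = 13 draws.
- At 17 draws, 52/17 = 3.06 mL per draw.

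Thirteen draws can be reached in two ways: by counting the first block once instead of for two days (4 + 6 + 3 = 13), or by counting the second block once instead of for three days (8 + 2 + 3 = 13). Either slip would give 52 mL. The protocol does not say how the figure was obtained, and the finding does not depend on it.

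**The case against.** The best counter-argument is that section 5.1.1 is not contradictory taken alone. It caps each draw at 4 mL, and seventeen draws averaging 3.06 mL would respect both the cap and the 52 mL total. This is true as far as it goes, so the conflict is strictly between the 52 mL total and the flat 4 mL of Appendix 4. But no volume near 3 mL appears anywhere in the protocol. Section 5.1.1 itself uses 4 mL as the working volume when it allows other drugs up to 20 samples of that size. A total offered as a limit should also cover the most that the schedule permits, and that is 68 mL.

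A second argument is that Appendix 4 does not itself list seventeen draws. Its first two blocks show four rows and two rows without saying that they repeat each day. Read literally, with three weekly samples, it gives 4 + 2 + 3 = 9 draws, or 36 mL, which is below 52 mL. It is right that the seventeen comes from the daily counts in 5.1.1(d) and the weekly draws in 5.1.1(e), with Appendix 4 supplying only the volume. The nine-draw reading, however, contradicts the stated seventeen and does not yield 52 mL either.

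Third, the commitment is worded mainly as one about the number of samples, with the volume in a nested parenthesis, and the number is correct. This stands. It is the reason to keep all seventeen draws and treat the volume as the error, and it limits the weight of the point.

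The consequence is also small. Section 2.4.2.1 limits this cohort to no more than ten participants per drug, chemical or drug class and plans no recruitment under 18. Even 68 mL is modest beside the up to 180 mL a year that Appendix 2 allows for adult cases and controls.

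**Conclusion.** The concern holds, as a minor one. Seventeen samples and 52 mL cannot both be right at 4 mL per draw. The schedule takes 68 mL, so the stated total is 16 mL too low and a completed schedule exceeds it by 31%.

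This rests on two readings: that the daily and weekly counts in 5.1.1(d) and (e) apply in full, which the stated seventeen confirms, and that draws are taken at the 4 mL of Appendix 4. If sites in practice drew about 3 mL, the 52 mL total could be met, but nothing in the protocol directs them to. The effect is confined to the stated blood volume for a small adult sub-study and has no bearing on inference.

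**What to change.** The sponsor should first confirm which figure was intended.

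- **If 4 mL per draw is intended (the more likely case):** replace 52 with 68 mL in the closing paragraph of section 5.1.1 and keep all seventeen samples, including the three weekly clearance draws. This is a one-number correction with no effect on the design or the assay. The stated burden rises by 16 mL, so any participant information that repeats the old total (not seen here) should be brought into line.
- **If 52 mL is a true ceiling:** set the draw volume to at most 3 mL in 5.1.1(b), (d) and (e) and throughout the beta-lactam schedule in Appendix 4. The total is then 17 × 3 = 51 mL. The cost is 25% less blood per draw for the plasma bioanalysis, so the laboratory should confirm that 3 mL is enough.

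Under either option, marking the first two blocks of Appendix 4 as per-day schedules would make the appendix yield the same seventeen draws as section 5.1.1.

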### **5.1.2 Patient Visit Schedule**

*5.1.2.1 Patient Visit Schedule for Drug Class NOS studies – see Appendix 2*

*5.1.2.2 Patient Visit Schedule for Oncological Immunotherapy studies – see Appendix 3*

*5.1.2.3 Patient Visit Schedule for Pharmacokinetic Sub-study- see Appendix 4*

### **5.2.1 Microbiome Sampling**

#### *5.2.1.1 Gut Microbiome*

The gut microbiome will be characterized via the collection of faecal samples according to standard operations procedures. The will then undergo sequencing analysis characterize bacterial populations during treatment and toxicity. Samples may also be taken during a clinically indicated flexible sigmoidoscopy.

#### *5.2.1.2 Oral Microbiome*

The oral microbiome will be characterized via the collection of oral cavity swab samples/ 5ml saliva according to standard operations procedures. The will then undergo sequencing analysis characterize bacterial populations during treatment and toxicity.

#### *5.2.1.3 Skin Microbiome*

Protocol V17 07.02.2023

The skin microbiome will be characterized via the collection of skin swabs (upto 3 areas) according to standard operations procedures. The will then undergo sequencing analysis characterize bacterial populations during treatment and toxicity.

### **5.3 Tissue Sampling**

Given the off-target end-organ immunopathophysiology of adverse events, further mechanistic insight can be gained through the collection of tissue samples from the end-organ site of toxicity involved.

#### **5.3.1 Colonic Biopsy**

Collection of colonic tissue samples is considered standard of care for diagnostic purposes in the case of colitis and forms part of the clinical care algorithm for CPI induced colitis. Sampling for this study would occur during a clinically indicated endoscopy but we would request a further biopsy samples (up to 12 in number) to be taken for research purposes. This will allow comprehensive sampling, even if the inflammation is patchy. These would be placed in either in cell medium and processed fresh or appropriate freezing media with a view to future work using cytometry techniques and other forms of cellular/ cytokine analysis or analysis of bacteria or proteins or genes. Additionally a request for permission to retrieve the clinical blocks after clinically indicated analyses have been performed will be made and histopathological/ immunohistochemical analysis performed. The patients will also have a paired bloods sample taken (50mls) at the time of endoscopy. **NO** endoscopic procedures would be undertaken for research purposes alone.

There may be some minor but short-lasting discomfort from having a blood test. Patients will not feel the biopsies being taken. There is a very small risk of complications (such as bleeding or perforation) from having any biopsy of the bowel, but it is important to note that the biopsy will be taken by an experienced endoscopist and will be done at sites with extensive endoscopic experience with established clinical practice. If patients have experienced colitis but are unable to give endoscopy samples a single (upto 50mls) blood sample can be given as part of the colitis substudy.

#### **5.3.2 Skin Biopsy**

Skin biopsies will be taken from patients who have skin hypersensitivity following any drug treatment including treatments used in oncology e.g CPIs, targeted treatments and chemotherapy (with a paired blood sample (up to 50mls)). If patients receiving CPIs wish to only give a blood sample and not a biopsy they will be approached for enrolment in the case control oncological immunotherapy study arm. If patients have experienced skin toxicity but are unable to give/do not wish to give skin biopsy samples a single (up to 50mls) blood sample can be given as part of the skin substudy.

Patients will only be given Patient Information Sheet A if they agree to have a skin sample taken. Otherwise patients will be given a PIS for the case control study. Blood and skin biopsy samples will be collected for research purposes. In a Stevens Johnson Syndrome (SJS) Patient and Public Involvement (PPI) group meeting held at the Wolfson Centre for Personalised Medicine (University

Protocol V17 07.02.2023

of Liverpool), the concept of skin biopsies for purposes of research was discussed. All SJS/PPI members were consulted and were unanimously in favour of biopsies being conducted in order to increase knowledge about cutaneous hypersensitivity reactions.

The Biopsy procedure shall take place either in out-patient Dermatology or Oncology Clinics at experienced centres, on the ward, or established Clinical Research Units (CRU). This will involve a simple procedure performed by a trained health professional whereby a full skin examination will be performed and classified. Subsequently up to two punch biopsies (up to 6mm) shall be taken from the reaction area and non-involved skin. If patients wish only to give a single punch biopsy then this will be taken from the involved skin. If patients develop reactions involving the scalp i.e. alopecia or folliculitis then we will ask the patient if they would be willing to have two smaller punch biopsies (up to 5mm) taken from the scalp in addition to the punch biopsy of normal skin. The rationale for this is that histological evaluation of immune reactions surrounding the hair follicle requires both vertical and horizontal sectioning which cannot be performed from a single biopsy. 50mls of blood and plucked hair follicles (up to 20) may be taken from the scalp for biomarker studies. If a patient has a blistering rash then the blister fluid (up to 5mls) can be taken either without or alongside a punch biopsy. Clinical photographs may be taken.

Skin biopsies/blood samples may also be taken following resolution of the hypersensitivity reaction to increase our mechanistic understanding and to compare with earlier samples. All skin biopsies shall be taken in line with appropriate Trust policy. Additionally, a request for permission to retrieve the clinical blocks after clinically indicated analyses have been performed will be made and histopathological/ immunohistochemical/transcriptomic analysis performed.

Patients may be asked to complete a 5 minute questionnaire to assess the impact of their skin on their quality of life. This assessment is known as the Dermatology Life Quality Index Questionnaire (DLQI) and is a validated questionnaire used regularly in dermatology outpatient clinics.

In order to understand the processes occurring in skin from patients experiencing adverse drug reactions (ADRs), it is important to analyse healthy skin from donors. This allow us to compare healthy skin biology with that of ADR skin to identify markers or signatures of ADRs. It also allows us to undertake studies using explants (excised skin tissue cultured in the laboratory), in which we can replicate the blistering skin ADR conditions in healthy skin. This will give us insight into the mechanisms at play but also allow us investigate novel therapies for blistering skin reactions.

Skin biopsies will be obtained from excess skin tissue collected from patients already undergoing excisions as part of their routine dermatology care. Patients will be identified and approached by their attending dermatologist who will also obtain informed consent. The collected skin will be utilised in *ex-vivo* experimental investigations examining factors that predispose individuals to adverse drug reactions. In order to further investigate biological risk factors and mechanisms of ADRs in the skin, biopsies will additionally be obtained, subject to informed consent, from individuals who have previously experienced a skin ADR.

